11.2 Analysis of Adverse Events

11.2.1 Treatment-Emergent Adverse Events

Treatment-emergent adverse events (TEAEs) are defined as any event with an onset that is after the first dose of study drug and with an onset date within 105 days after the last dose of study drug in the analysis period, or prior to the first dose in the subsequent period for subjects who entered in to the subsequent period. Events where the onset date is the

same as the study drug start date are assumed to be treatment-emergent, unless the adverse event start time is prior to the study drug start time. If an incomplete onset date is collected for an adverse event, the event will be assumed to be treatment-emergent unless there is other evidence that confirms that the event is not treatment-emergent (e.g., the event end date is prior to the study drug start date).

Treatment-emergent adverse events (TEAE) for each safety population are defined as follows:

TEAEs of Safety_A:

For subjects who do not enter Part B, TEAEs are defined as any event with an onset after the first dose of study drug and no more than 105 days after the last dose of study drug.

For subjects who enter Part B, TEAEs are defined as any event with an onset after the first dose of study drug in Part A and before the first dose of study drug in Part B.

TEAEs of Safety_B_RR, Safety_B_R, Safety_B_NR:

TEAEs are defined as any event with an onset after the first dose of study drug in Part B and no more than 105 days after the last dose of study drug in the study.

TEAE of ALL_RZB:

TEAEs are defined as any event with an onset after the first dose of risankizumab and no more than 105 days after the last dose of risankizumab in the study.

The number and percent of subjects experiencing treatment-emergent TEAEs will be tabulated using the Medical Dictionary for Drug Regulatory Activities (MedDRA®) system organ class and preferred term.

Summary tables will be presented as follows:

1. Adverse Event Overview

The number and percentage of subjects experiencing treatment-emergent adverse events will be summarized for the following adverse event categories:

- Any AE
- Any AE that was assessed as related to study drug by the investigator
- Any severe AE
- Any serious AE (SAE)
- Any serious AE that was assessed as related to study drug by the investigator
- Any AE leading to discontinuation of study drug
- Any AE leading to death
- Any deaths
- Areas of Safety Interest

2. Adverse Events by System Organ Class and Preferred Term

TEAEs will also be summarized and presented using primary Medical Dictionary for Regulatory Activities (MedDRA version 16.1 or later version) system organ classes (SOCs) and preferred terms (PTs). The SOCs will be presented in alphabetical order, and the PTs will be presented in alphabetical order within each SOC.

Subjects reporting more than one adverse event for a given MedDRA preferred term will be counted only once for that term (most severe incident for the severity tables and most related incident for the relationship tables). Subjects reporting more than one type of adverse event within a SOC will be counted only once for that SOC. Subjects reporting more than one type of adverse event will be counted only once in the overall total.

In addition, the number and percentage of adverse events with causal relationship between the events and the study drug will be summarized using the same conventions described above.

3. Adverse Events by Maximum Severity

The severity grading of AEs follows Rheumatology Common Toxicity Criteria (RCTC).

- Grade 1 – mild
- Grade 2 – moderate
- Grade 3 – severe
- Grade 4 – life threatening

Adverse events will also be summarized by maximum severity. If a subject has an adverse event with unknown severity, then the subject will be counted in the severity category of "unknown," even if the subject has another occurrence of the same event with a severity present. The only exception is if the subject has another occurrence of the same adverse event with the most extreme severity – ("Life-threatening"). In this case, the subject will be counted under the "Life-threatening" category.

4. Adverse Events by Maximum Relationship

Adverse events will be summarized by maximum relationship to study drug, as assessed by the investigator. Relationship of an AE to study drug is assessed by the investigator and collected in the CRF as 'Yes' or 'No.' If a subject has an adverse event with unknown relationship, the subject will be counted in the relationship category of "unknown," even if the subject has another occurrence of the same event with a relationship of "No." If the subject has another occurrence of the same adverse event with a relationship assessment of "Yes," the subject will be counted under the "yes" category.

A listing of all pretreatment (i.e., events start prior to the first study drug injection) serious adverse events will be provided.

The following tables are planned.

Treatment-emergent adverse events will be summarized as follows:

- Grouped by SOC and PT
- Grouped by SOC, PT and maximum relationship to study drug
- Grouped by SOC, PT and maximum severity

Treatment-emergent serious adverse events will be summarized as follows:

- Grouped by SOC and PT
- A by-subject listing will be provided

Pre-treatment serious adverse events will be summarized as follows:

- A by-subject listing will be provided

Treatment-emergent adverse events leading to death or premature discontinuation of study drug will be summarized as follows:

- Grouped by SOC and PT
- Separate listings by subject for deaths and premature terminations of study drug due to adverse events will be provided.

Treatment-emergent areas of safety interest will be summarized as follows:

- Grouped by SOC and PT
- A listing by subject will be provided.

Areas of Safety Interest:

Areas of Safety Interest groupings are listed in Table 21. These events are of interest due to a higher rate in the moderate to severe psoriasis population, or of interest for all Ig products or products in general (DILI).

The final list will be based on the most updated final version of risankizumab Product Safety Statistical Analysis Plan, which is consistent to the most updated risankizumab Risk Management Plan.

Table 21. Areas of Safety Interest

ASI Grouping	Categories (ASI)	Search Criteria	Terms to Display	Include in AE Overview (Y/N)
Adjudicated CV Events	Major adverse cardiovascular events (MACE)	Adjudicated events	Display underlined terms defined by the following adjudicated terms: 
 • CV Death which includes CETERM values: Fatal CV, Fatal PE, Fatal Non-Cardiac/Non-Neuro Arterial Thrombosis/Thromboembolism, Undetermined Death, Not assessable death (cardiac/neuro/thrombotic), Fatal Stroke • Myocardial infarction • Stroke 	Y
	Extended MACE	Adjudicated events	Display underlined terms from MACE and underlined terms below: 
 • Hospitalization for Unstable Angina • Coronary Revascularization Procedures 	N

Table 21. Areas of Safety Interest (Continued)

ASI Grouping	Categories (ASI)	Search Criteria	Terms to Display	Include in AE Overview (Y/N)
Adjudicated CV Events (continued)	Other CV events	Adjudicated events	Display underlined terms defined by the following adjudicated terms: 
 • Thrombotic events which includes CETERM values: Deep Vein Thrombosis, TIA, Pulmonary Embolism, Non-fatal Non-Cardiac/Non-Neurological Arterial Thrombosis/ Thromboembolism, Other Venous Thrombosis, specified (non-fatal) • Cardiac arrhythmia which includes CETERM of: Clinically Significant Arrhythmia • Congestive heart failure which includes CETERM of Heart Failure • Hypertensive emergency 	N
Serious infections, TB, fungal and opportunistic infections (including herpes zoster)	Serious infections	Serious PTs of the CMQ (company MedDRA query) Infections (CMQ 8000018)	PTs	Y
	TB	Tuberculosis (including Investigations) CMQ (code 80000033)	PTs	Y
	Opportunistic infections	Opportunistic infections CMQ (code 80000073)	PTs	N

Table 21. Areas of Safety Interest (Continued)

ASI Grouping	Categories (ASI)	Search Criteria	Terms to Display	Include in AE Overview (Y/N)
Serious infections, TB, fungal and opportunistic infections (including herpes zoster) (continued)	Fungal infections	Fungal infections CMQ (code 80000063)	PTs	N
	Herpes Zoster	Herpes zoster CMQ (code 80000175)	PTs	N
Malignancies	All possible malignancies	Narrow – Malignancies (SMQ 20000090)	PTs	N
	Malignant Tumours	Narrow – Malignant tumours (SMQ 20000194)	PTs	Y
	Non-melanoma skin cancer (NMSC)	Broad – Skin malignant tumours (SMQ 20000204) excluding terms identified by the Melanoma CMQ (code 80000119)	PTs	N
	Malignant Tumours excluding NMSC	'Malignant Tumours excluding NMSC' is identified by the 'Malignant Tumours' search excluding terms identified by the 'Non-melanoma skin cancer' (NMSC) search.	PTs	Y
Hypersensitivity Reaction	Hypersensitivity	Narrow – Hypersensitivity (SMQ 20000214)	PTs	Y – serious events only

Table 21. Areas of Safety Interest (Continued)

ASI Grouping	Categories (ASI)	Search Criteria	Terms to Display	Include in AE Overview (Y/N)
Hypersensitivity Reaction (continued)	Anaphylactic Reaction	Narrow – Anaphylactic reaction (SMQ 20000021)	PTs	N
Hepatic Events	Hepatic Events	Broad – Hepatic failure, fibrosis and cirrhosis and other liver damage-related conditions (SMQ 20000013) Broad – Hepatitis, non-infectious (SMQ 20000010) Broad – Cholestasis and jaundice of hepatic origin (SMQ 20000009) Broad – Liver related investigations, signs and symptoms (SMQ 20000008) Narrow – Liver-related coagulation and bleeding disturbances (SMQ 20000015)	PTs	N

Adverse Event per 100 Patient-Years of Exposure

Adverse events occurring during the entire study will be presented by event rate per 100 patient-years. These will be presented for any TEAEs, serious adverse events, Areas of Special Interest.

AEs per 100 patient-years of exposure is defined as the number of AEs divided by the total exposure in 100 patient-years. Note that one event per preferred term per day per subject will be counted in the calculation of the number of AEs (i.e., a preferred term will not be counted twice on the same day for the same subject). See the calculation method below.

$$100 \times \frac{\text{Number of TEAEs}}{\text{Total Patient Years}}$$

where total patient years is defined as the sum of the study drug exposure (defined as date of last dose – date of first dose + 105 days (5 half-lives)) of all subjects normalized by 365.25, and rounded to one decimal place.

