7.3.4 Safety analyses

Adverse events will be coded using the Medical Dictionary for Regulatory Activities (MedDRA) coding dictionary. Standard AbbVie summary tables and listings will be produced. All adverse events with an onset between start of treatment and end of the residual effect period (REP), a period of 15 weeks after the last administration of BI 655066 (active or placebo), will be assigned to the treatment period for evaluation.

All treated patients will be included in the safety analysis. In general, safety analyses will be descriptive in nature and will be based on AbbVie standards. No hypothesis testing is planned.

Statistical analysis and reporting of adverse events will concentrate on treatment-emergent adverse events. To this end, all adverse events occurring between start of treatment and end of the residual effect period will be considered 'treatment-emergent'. The residual effect period is defined as 15 weeks. Adverse events that start before first drug intake and deteriorate under treatment will also be considered as 'treatment-emergent'.

Frequency, severity, and causal relationship of adverse events will be tabulated by system organ class and preferred term after coding according to the current version of the Medical Dictionary for Drug Regulatory Activities (MedDRA).

Laboratory data will be analysed both quantitatively as well as qualitatively. The latter will be done via comparison of laboratory data to their reference ranges. Values outside the reference range as well as values defined as clinically relevant will be highlighted in the listings. Treatment groups will be compared descriptively with regard to distribution parameters as well as with regard to frequency and percentage of patients with abnormal values or clinically relevant abnormal values.

Vital signs, physical examinations, or other safety-relevant data observed at screening, baseline, during the course of the trial and at the end-of-trial evaluation will be assessed with regard to possible changes compared to findings before start of treatment.

More information about the safety analysis will be provided in the TSAP.

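### The SAP defines treatment-emergent adverse events by onset alone and, without declaring it, drops the protocol's rule for events that start before dosing and worsen on treatment

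*SAP*

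**What the plan says.** Protocol 7.3.4 gives two routes to treatment-emergent status. The first covers events occurring from the start of treatment until the residual effect period ends: "The residual effect period is defined as 15 weeks". The second covers earlier events: "Adverse events that start before first drug intake and deteriorate under treatment will also be considered as" treatment-emergent.

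SAP 11.2.1 gives only the first. The general definition begins "Treatment-emergent adverse events (TEAEs) are defined as any event with an onset that is after the first dose of study drug" and closes the window 105 days after the last dose, or at the first dose of the next period. Events on the dosing day count "unless the adverse event start time is prior to the study drug start time". For the Part B safety populations it lists, "TEAEs are defined as any event with an onset after the first dose of study drug in Part B". For all patients treated with risankizumab (ALL_RZB), "TEAEs are defined as any event with an onset after the first dose of risankizumab"; here the window closes 105 days after the final risankizumab injection.

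SAP 14.1 lists four changes from the protocol. The only one on safety is the pre-specification of areas of safety interest.

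**The concern.** Adverse events are collected from informed consent (Protocol 5.3.7), and screening runs from 42 to 7 days before Day 1 (Protocol flow chart). Event records with a pre-dose onset will therefore exist. Suppose such an event is mild in screening, becomes severe after the first dose, and stays on one record. It is treatment-emergent under the protocol and not under the SAP.

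The TEAE definition feeds the adverse event overview, the tables by system organ class and preferred term, the maximum-severity and maximum-relationship tables, and the rates per 100 patient-years. SAP 11.1 also plans Fisher's exact tests between arms in Safety_A and Safety_B_RR. A narrower definition that is not declared changes what those tables mean, and in the direction of fewer events.

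**Working it through.** The plan gives no figure to reproduce, so the check is a comparison of texts followed by a statement of scale.

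1. **Length of the window.** Protocol: 15 weeks × 7 = 105 days. SAP: 105 days. The lengths agree. The anchors do not: the protocol counts from the last risankizumab injection (active or placebo), while the SAP's general and Part B definitions count from the last dose of study drug. That is a separate matter to reconcile. The comparison below holds the window fixed.

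2. **Onset after first dose.** Both documents count it.

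3. **Onset before first dose, worsening after it.** Protocol 7.3.4 counts it. In SAP 11.2.1 the general definition, the same-day rule, the incomplete-date rule and the definitions for Safety_A, for Safety_B_RR, Safety_B_R and Safety_B_NR, and for ALL_RZB all depend on onset. None mentions worsening or a rise in grade.

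4. **Does another part of the SAP restore the rule?** No. The maximum-severity tables grade events already classed as treatment-emergent. Pre-treatment serious events get a by-subject listing, and SAP 11.2.2 lists deaths and all serious events. Those outputs keep serious cases visible but do not put them into TEAE counts. A non-serious pre-dose event that worsens has no summary planned for it as such.

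5. **Is the departure declared?** Not in SAP 14.1. SAP 11.3.2 does openly declare another safety departure, the use of NCI CTCAE instead of RCTC for grading laboratory values.

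6. **Direction.** With the window fixed, the SAP's set of events is the protocol's set less those in step 3. The omission can lower a TEAE count or leave it unchanged. It cannot raise one.

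7. **Scale.** Let *p* be the proportion of patients with a pre-dose event that worsens in the window, and *q* the share of those kept under the original onset. The expected number of patients affected per arm in Part A is 300 × *p* × *q*. Neither quantity is in the documents. As assumptions: *pq* = 0 gives 0; *pq* = 1% gives 300 × 0.01 = 3; *pq* = 2% gives 300 × 0.02 = 6. A patient with another TEAE is already in the any-event row, so the loss falls mainly on the preferred-term and severity tables.

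**The case against.** The strongest reply is that the data may already capture these cases. Protocol 6.2.1 puts chronic diseases and current conditions on a Baseline Condition page, apart from the adverse event page. Protocol 5.3.7 requires worsening of the underlying disease or of other existing conditions to be recorded as an adverse event. If that entry carries an on-treatment onset, the SAP counts it. This stands in part: the undercount is conditional. But neither document says which onset date such an entry receives, and no rule covers an adverse event already open that rises in grade. The exposed group is chiefly events arising between consent and first dose that keep their first onset date.

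A second reply is that the protocol describes safety analysis as descriptive, based in general on AbbVie standards, with more detail to come in the analysis plan. This lowers the stakes, since no primary or key secondary test is affected. It does not remove the contradiction, because the same protocol section keeps the specific worsening rule.

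A reader might also infer that the loss is greatest after the switch to risankizumab, since an event that begins on adalimumab in Part A and worsens afterwards is not a TEAE in the Part B or ALL_RZB tables. The documents do not support calling that a breach of the protocol. Its clause covers events before first drug intake, and an event starting on adalimumab comes after that point. Such an event is already counted in Safety_A. Nothing in the documents shows that the effect is larger there.

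**Conclusion.** The contradiction is established from the text: a rule stated in Protocol 7.3.4 is absent from SAP 11.2.1 and the departure is not declared in SAP 14.1. TEAE counts, including severe and serious TEAE counts, fall below the protocol's definition wherever a worsening stays under its pre-dose onset. The size is unknown, and is zero if every worsening becomes a new record with its own onset.

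It would be too strong to say that on-treatment worsening is certainly undercounted, or that serious cases vanish. The first depends on recording practice that the documents do not settle, and the second is answered by the listings. Laboratory worsening is also assessed apart from event onset, through shift tables and the criteria for potentially clinically important values. The point should be corrected before database lock, but it does not threaten the efficacy conclusions.

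**What to change.** Add to SAP 11.2.1 a sentence to this effect: *An adverse event with onset before first study drug intake that increases in grade or becomes serious after the first dose, within the TEAE window, is treatment-emergent.*

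State beside it how worsening is identified from the eCRF: by a new record with its own onset, or by a change in severity on the existing record. This matters because no document shows that the date of a grade change is collected. Protocol 5.3.7 names onset, end date and intensity only as examples of what is recorded.

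As a consistent extension beyond the explicit protocol text, apply the same rule at the first Part B dose and, for ALL_RZB, at the first risankizumab dose, so that events worsening after the switch are counted there. If the onset-only definition is intended, declare it in SAP 14.1 with a reason.

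The cost is one SAP sentence with its identification rule, modest programming, and possibly slightly higher TEAE counts.

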6.0 Analysis Conventions

Definition of Baseline:

The last non-missing measure collected on or before the date of the first dose of study drug injection will be used as Baseline for summary of demographics and disease characteristics, efficacy analyses, and safety analyses in each period, with the exception that:

- The last evaluation on or prior to the first dose date of risankizumab will be used for the safety analyses for ALL_RZB populations.
- For all vital sign assessments, only assessments prior to first dose time will be considered, since vital signs are to be assessed both pre- and post-dose in some visits.

For subjects who are randomized but do not take any study drug during the study, the last non-missing measurement collected on or before the date of randomization will be used as Baseline.

Definition of Final Observation (Applicable to Safety Analyses):

Final observation for the Part A is defined as:

- The last non-missing observation collected within 105 days following the last dose of study drug in Part A for subjects who were not dosed in Part B.
- The last non-missing observation collected on or before the first dose date of study drug on or after Week 16 and within 105 days following the last dose of study drug in Part A for subjects who were dosed in Part B. For vital sign assessments, only assessments prior to the first dose of study drug injection in Part B will be included in the analysis for Part A.

Final observation in Part B and in the entire study is defined as the last non-missing observation collected within 105 days after the last dose of study drug.

Definition of Rx Days (Days Relative to the Date of First Dose of Study Drug)

Rx days are calculated for each time point relative to the date of first dose of study drug. They are defined as the number of days between the day of the first dose of study drug and the specific time point. Rx days are negative values when the time point of interest is prior to the first study drug dose day. Rx days are positive values when the time point of interest is on or after the first study drug dose day. The day of the first dose of study drug is defined as Rx Day 1, while the day prior to the first study drug dose is defined as Rx Day -1 (there is no Rx Day 0).

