Week 44	197	[142, 211]
Week 48 (EOT + 4 Weeks)	225	[212, 239 ^a]

Rx Day calculated relative to the first dose of study drug in Part B. For subjects re-randomized but not dosed in Part B, Rx Day calculated relative to the IRT date of re-randomization evaluation.

a. The minimum of upper bound and 105 days of last dose for safety analyses.

Table 10. Visit Windows for Vital Signs for Part B (Safety_B_RR Population)

Window Label	Target Day	Time Window
Entry of B	1	≤ 1
Week 20	29	[2, 43]
Week 24	57	[44, 71]
Week 28	85	[72, 99]
Week 32	113	[100, 127]
Week 36	141	[128, 155]
Week 40	169	[156, 183]
Week 44	197	[184, 211]
Week 48 (EOT + 4 Weeks)	225	[212, 239 ^a]

Rx Day calculated relative to the first dose of study drug in Part B. For subjects re-randomized but not dosed in Part B, Rx Day calculated relative to the IRT date of re-randomization.

a. The minimum of upper bound and 105 days of last dose for safety analyses.

Table 11. Visit Windows for Other Efficacy Endpoints Only Collected at Week 44 in Part B (ITT_B_RR/ITT_B_R/ITT_B_NR/ITT_B_RZB/PP_B_RR Populations)

Window Label	Target Day	Time Window
Entry of B	1	≤ 1
Week 44	197	[2, 393]

Rx Day calculated relative to the first dose of study drug in Part B. For subjects re-randomized but not dosed in Part B, Rx Day calculated relative to the IRT date of re-randomization.

Table 12. Visit Windows for Local Tolerability for Part B (Safety_B_RR Population)

Window Label	Target Day	Time Window
Week 28	85	[2, 141]
Week 44	197	[142, 253 ^a]

Rx Day calculated relative to the first dose of study drug in Part B. For subjects re-randomized but not dosed in Part B, Rx Day calculated relative to the IRT date of re-randomization.

a. The minimum of upper bound and 105 days of last dose for safety analyses.

Note. There is no local tolerability at re-randomization and after EOT.

Table 13. Visit Windows for Laboratory and ECG Parameters for ALL_RZB Population

Window Label	Target Day	Time Window
Baseline	1	≤ 1
Week 4	29	[2, 71]
Week 16	113	[72, 155]
Week 28	197	[156, 253]
Week 44	309	[254, 323]
Week 48 (EOT + 4 Weeks)	337	[324, 351 ^a]

Rx Day calculated relative to the first dose of risankizumab.

a. The minimum of upper bound and 105 days of last dose of risankizumab for safety analyses.

Table 14. Visit Windows for Vital Signs for ALL_RZB Population

Window Label	Target Day	Time Window
Baseline	1	$\leq 1^a$
Week 4	29	[2, 43]
Week 8	57	[44, 71]
Week 12	85	[72, 99]
Week 16	113	[100, 127]
Week 20	141	[128, 155]

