11.2.2 SAEs (Including Deaths) and Adverse Events Leading to Study Drug Discontinuation

Deaths and all SAEs will be presented in listing format. In addition, SAEs and AE leading to study drug discontinuation will be summarized by System Organ Class and MedDRA Preferred Term.

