11.3 Analysis of Laboratory Data

For the assessments of laboratory data, values observed more than 105 days after the last dose of study drug will be excluded.

Listing and descriptive statistics of laboratory values over time, changes from baseline, and extreme abnormal value on treatment will be provided. Extreme abnormal value is the value which is most significantly away from the reference range. Frequency of subjects with transitions relative to reference range and listing of subjects with significant abnormal laboratory values will be presented as well.

Analyses will be conducted in the Safety_A Population, the Safety_B_RR Population, and the ALL_RZB Population.

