11.6 Local Tolerability

Local tolerability of the subcutaneous injection will be assessed by the investigator according to 6 items: swelling, induration, heat, redness, pain, and other findings. Proportion of subjects reporting each condition will be analyzed.

Analyses will be conducted in the Safety_A Population and the Safety_B_RR Population. In addition, the overall rate (with at least one occurrence) during the study will also be presented in the ALL_RZB Population.

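### In the continuing risankizumab arm, SAP 11.2.1 stops counting ALL_RZB adverse events at Day 302, before Week 44 and 28 days short of the protocol's on-treatment end, and SAP 14.1 does not list the change

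*SAP*

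**What the plan says.** SAP 11.2.1 opens with a general rule: an event must start "within 105 days after the last dose of study drug in the analysis period". It then gives windows by population. One definition, headed "TEAEs of Safety_B_RR, Safety_B_R, Safety_B_NR", counts from study drug. None is given for the Part B safety population of the continuing arm, so the general rule applies there. For ALL_RZB the window is "after the first dose of risankizumab and no more than 105 days after the last dose of risankizumab in the study".

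Protocol 5.3.7 defines the residual effect period as 15 weeks after the last BI 655066 injection and says that placebo injections count. Protocol 7.3.4 repeats this for the safety analysis.

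SAP 5.1 plans complete safety tables for Safety_A, Safety_B_RR and ALL_RZB, and AE overviews for the other safety populations.

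Three visit-window tables for ALL_RZB in SAP 6.0 carry a matching cap, "The minimum of upper bound and 105 days of last dose of risankizumab for safety analyses": on the Week 48 row of Table 13 (laboratory, ECG) and Table 14 (vital signs), and on the Week 44 row of Table 15 (local tolerability). SAP 11.3 has a different laboratory rule: "values observed more than 105 days after the last dose of study drug will be excluded". The final observation in SAP 6.0 is also tied to study drug: "the last non-missing observation collected within 105 days after the last dose of study drug".

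SAP 14.1 lists four changes from the protocol: population definitions, the Part B test hierarchy, PASI 100 at Week 44, and areas of safety interest.

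**The concern.** Patients who continue on risankizumab receive dummy risankizumab at Week 32. The protocol's clock starts from that injection; the SAP's ALL_RZB clock starts four weeks earlier, from the last active dose. The SAP window therefore closes while these patients are still in the protocol's treatment period.

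ALL_RZB is the only population in which this arm's Part B events are tabulated in full by system organ class, preferred term, severity and relationship. Events that the protocol calls on treatment would be absent from those tables, and a reader of SAP 14.1 would not know. The same cap in the window tables defines rows that no patient on schedule can fill.

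**Working it through.** **Inputs.** Active risankizumab in the continuing arm is given at Weeks 0, 4, 16 and 28, with placebo at Weeks 20 and 32. Switched patients get active doses at Weeks 16, 20 and 32 (protocol 3.1 and Table 4.1.1: 1; SAP 4.2). The last adalimumab or dummy injection is at Week 41 (protocol Table 4.1.4: 2).

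**Reproducing the plan's days.** Day = 7 × week + 1 gives Week 28 = 197, Week 32 = 225 and Week 44 = 309, as in the protocol's visit table and flow chart. Week 41 = 288 and Week 48 = 337. Fifteen weeks × 7 = 105 days, as in the SAP.

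**Which dose counts.** In the ALL_RZB rule, risankizumab must mean active drug. Membership requires a 150 mg dose, SAP 4.2 names the dummies separately, and counting placebo would start a switched patient's window on Day 1 of adalimumab.

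**End of window, continuing arm.**

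| Rule | Last dose counted | End |
|---|---|---|
| SAP 11.2.1, ALL_RZB | Day 197, active | 197 + 105 = 302 |
| Protocol 5.3.7, 7.3.4 | Day 225, active or placebo | 225 + 105 = 330 |
| SAP general rule, dummies included | Day 288 | 288 + 105 = 393 |

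The gap to Week 44 is 309 − 302 = 7 days; the gap to the protocol is 330 − 302 = 28 days. With ±3-day visit windows the latest cutoff is 200 + 105 = 305 and the earliest Week 44 visit is 306, so every on-schedule patient is affected. Switched patients end at 225 + 105 = Day 330 under both the ALL_RZB and the protocol rule.

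**Days left out.**
- Rollover patients have no visit after Week 44: Days 303-309, or 7 of 308 days (2.3%).
- Other completers: Days 303-330, or 28 of 329 days (8.5%).
- Assuming 300 completers: 7 × 300 / 365.25 = 5.7 patient-years if all roll over; (7 × 150 + 28 × 150) / 365.25 = 14.4 if half do; 28 × 300 / 365.25 = 23.0 if none do. The documents do not give the rollover share.

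**Window tables.**
- Tables 13 and 14, Week 48: the window [324, 351] becomes [324, 302], which is empty. Reaching Day 324 would need a Week 28 dose on Day 219 or later (324 − 105). Switched patients count from their first active dose, so Week 48 is only Rx Day 225 for them.
- Table 15, Week 44: the window becomes [254, 302], which excludes Day 309. The switched arm's Week 44 visit is Rx Day 197 and falls in the uncapped Week 28 row [156, 253]. No scheduled assessment reaches the Week 44 row.

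**Patient-year denominator.** SAP 11.2.1 uses last dose − first dose + 105. If last dose means active risankizumab, this is 197 − 1 + 105 = 301 days, the same span as the event window. If it includes adalimumab dummies, it is 288 − 1 + 105 = 392 days against a 301-day event window, and the arm's rate is understated by 1 − 301/392 = 23.2%. SAP 9.0 measures ALL_RZB exposure from risankizumab injections, which favours the first reading, but 11.2.1 does not say.

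**The case against.** The best defence is that this is a coherent choice. ALL_RZB is the SAP's own population: it is entered by active exposure and its safety baseline is taken at the first risankizumab dose. An active-drug clock of 105 days, which the SAP equates with 5 half-lives, fits that purpose. Protocol 7.3.4 also refers to company standards and leaves further detail to the analysis plan. The pharmacological rationale stands, and it is why the active-drug cutoff should be kept as a sensitivity table. But protocol 7.3.4 itself fixes the period and says placebo injections count. A plan that shortens that period should say so.

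A reader might infer that the SAP contradicts itself because an event on Day 305 could be treatment-emergent in the arm's Part B overview but not in ALL_RZB. The documents do not support that. The SAP says openly that windows differ by population, and no treatment comparison is planned in ALL_RZB. The real mismatch is between the SAP 11.3 laboratory rule and the Table 13 footnote.

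A reader might also blame the empty Week 48 rows on the departure from the protocol. The protocol's own limit would give [324, 330] and still exclude the scheduled visit on Day 337. These rows need the study-drug rule or deletion.

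**Conclusion.** The point holds as a minor one. The ALL_RZB window in the continuing arm closes at Day 302, inside the treatment period and 28 days before the protocol's limit, and the change is not listed. Three window rows cannot be filled on schedule. No efficacy result or treatment comparison changes.

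Three stronger readings go too far:
- **That the events are lost.** They can still appear in the arm's Part B overview, and SAP 11.2.2 provides that "Deaths and all SAEs will be presented in listing format". The overview route assumes that study drug includes dummy injections. SAP 5.1 supports this by writing active study drug where it means active.
- **That the overall tolerability rate is wrong.** SAP 11.6 says that "the overall rate (with at least one occurrence) during the study will also be presented in the ALL_RZB Population". Whether the Table 15 windows restrict that rate is not stated, so the effect on it is open.
- **That the event rates are biased, or that they are safe.** Either depends on which doses define the last dose in the patient-year formula.

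The 28-day loss applies only to patients who do not roll over, so 23.0 patient-years is an upper bound under 300 completers.

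**What to change.** 1. In SAP 11.2.1 and the Table 15 footnote, count the ALL_RZB 105 days from the last risankizumab injection, active or placebo, as in protocol 7.3.4. Both arms then end at study Day 330, and the Table 15 Week 44 row returns to [254, 323]. Keep the active-drug cutoff as a sensitivity table. If the sponsor prefers it as the main rule, list it in SAP 14.1.
2. In Tables 13 and 14, apply the SAP 11.3 study-drug rule, so that the Week 48 window stays [324, 351], or delete the Week 48 rows. With the study-drug rule, state that the laboratory and vital-sign cap differs from the AE cap, because the two clocks will not match.
3. State which doses define the last dose in the patient-year formula, and match the denominator to the follow-up counted, cut at EOT for rollover patients. Without that cut, a rollover patient would contribute 329 days for 308 days of follow-up, understating the rate by 1 − 308/329 = 6.4%.
4. State in SAP 11.6 whether the Table 15 windows apply to the overall rate.

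The cost is one AE rule, three footnotes, one formula and one clarifying sentence, with no new data. The downside is that some added AEs fall more than 5 half-lives after active drug; the sensitivity table separates them. The added Week 44 tolerability visit follows dummy injections, but so does the Week 28 pre-dose assessment, which is already counted.
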